8.1. Sample size

20 newly recruited NMDARe patients and 20 patients from a previous pilot study for extended follow-up. Given that NMDARe is a rare disease, we are not able to perform a sample size estimation. We propose this sample size based on the feasibility according to our previous experience on the number of patients that we annually diagnosed in our centre and based on the results from the pilot study.

8.2. Statistical analyses

For human studies, we will analyze differences in cognitive and psychiatric variables between and within groups (newly recruited NMDARe patients and those from the pilot study) in the longitudinal follow-up using multilevel linear mixed-effect models, adjusting for group, age, sex, and socioeconomic status to control for possible confounds. Lme4 R package will be used to fit LME models, and residual plots will be used to validate them. Comparisons will be done with emmeans library and Tukey method for post-hoc correction for multiple testing. The global tendency of recovery of cognitive deficits in NMDARe (proportion of patients compared to the general population in each domain) will be assessed with the Cochran-Armitage test for trend; other comparisons within NMDARe will be done with Wilcoxon signed-rank and McNemar's tests. The patient behavioral, PSG and EEG data will be analyzed with linear regression using multiple regressors (task parameters, fraction of NREM N3, disease condition, with/without remote training, etc.). All analyses will be addressed considering a two-tailed type I error of 5% with statistical significance set at p-value <0.05, using SPSS (IBM Corp, Armonk, NY) and R package (Vienna).

For animal behavior studies with multiple determinations in time (e.g., new object recognition) we will use the double variance analysis (ANOVA). For behavior studies with a single determination in time (e.g., depressive behavior; "tail suspension") we will use the simple ANOVA. Electrophysiological studies (long-term potentiation) will be analyzed with double ANOVA. In all experiments, the post-hoc analysis will use the Bonferroni correction for multiple tests. A value of p <0.05 will be considered significant. The alpha-error will be set to 0.05. The analyses will be done using GraphPad Prism. Animal sample size: To detect a difference between the two groups with a 95% CI, assuming an estimated standard deviation of 20% for behavioral tests and a 20% procedural mortality, we will need 12 mice per group.

9. Risks and benefits for participants in the study

It is possible that patients will not benefit from participating in this study. However, based on the results of previous similar studies ("Immune-mediated diseases of the synapse: symptoms, brain networks, and the link to human memory", IP: [name], Code: HCB/2016/0596; "A Translational Model of Antibody-mediated Synaptic Disease: Symptoms, Neuronal Circuits, and the Mechanisms of Memory Loss and Recovery", IP: [name], Code: HCB/2018/0561) we expect that patients will directly and immediately benefit from their participation in the carefully monitored cognitive training program and the close clinical follow up in an experienced unit.

Our previous studies with this same load of tests in presential visits were successful and

patients with anti-NMDAR and anti-LGI encephalitides returned for the most part in successive retest sessions after 3, 6, 12 and even 24 months (Guasp et al. Lancet Neurology 2022; Ariño et al. Neurology 2020; Stein et al. Nat Commun 2020). This demonstrates that the load of tasks and frequency of visits was not unbearable and patients were happy to maintain participation in the project for an extended period of time and repeat sessions with identical task loads. We specifically gauged participant satisfaction in a gathering of participating families at Hospital Clínic in 2018, where we presented the objectives and initial results of the study and allowed participants to ask questions and express their concerns. Participants were very satisfied with the study and appreciated the opportunity to be monitored in the reference center for this disease in Europe, and to get in touch with other families afflicted by the same rare disease. We plan to repeat this experience in the framework of the present project in order to detect possible dissatisfactions with our experimental protocols and adapt them for the comfort of the participants.

Nonetheless, the detailed risks for each of the procedures in the current study are as follows:

- a) Risks of presential Neurologic, Psychiatric and Cognitive assessments: These evaluations are innocuous and do not represent any substantial risk for participants. The main risk of these evaluations is fatigue, and they may be demanding in terms of execution time, but patients will be able to take breaks during the testing to alleviate it. Moreover, they will be guided by a member of our team to ensure that it does not cause any major discomfort to the patient.
- b) Risks of remote Neurologic, Psychiatric and Cognitive assessments: These will be run either by telephone or via a video-conference (online platform link provided by us) at various time points during the participant monitoring (Fig. 1). The main risk is fatigue, but a member of our team will ensure that it does not cause any major discomfort to the patient.
- c) Risks of Magnetic Resonance Imaging (MRI): The known risks associated with MRI studies are minimal. The procedure uses radio waves and a magnetic field to take pictures. Some individuals may feel claustrophobic (uncomfortable in small areas) during the MRI scan or may be disturbed by the sounds of the machine (which are loud and repetitive). Patients can be given music to listen to during the scan or can hear the voice of the technician. These have been shown to help patients relax during the scan. If the subject experiences these feelings and is uncomfortable, they can always discontinue the scan
- d) Risks of presential EEG studies: EEG is considered a safe procedure and causes no discomfort. During the recording, subjects can relax. Some people may develop a mild rash where the electrodes were attached that resolves without treatment.
- e) Risks of presential Sleep studies: The same for EEG studies, as well as possible discomfort before falling asleep and reduced night rest. However, the cabling system is optimized to facilitate the free movement of patients at night, and the room is soundproofed.
- f) Risks of Psychophysical testing and Brain recordings (both presential and remote): These evaluations are innocuous and do not represent any substantial risk for participants. The main risk of these evaluations is fatigue, reduced night rest, and they may be demanding in terms of execution time. However, they will only be performed in the course of two weeks separated by 6 months, for each participant. The computerized task will have a game component to make it engaging, as well as the device is specifically designed to be comfortable during sleep for nocturnal recordings. In the first day of the week of recordings, a member of our team will make a video-conference with the participant (including family members if they are minors) to assist with the setup of the device for

testing and recording. Of note, the remote EEG device does not require complex setup or extensive preparations and it is easy to wear, as it consists of a cap with electrodes already attached that communicates wireless with the iPad tablet. Thus, there is no risk of mild rash. The cap may feel uncomfortable similar to that of a bathing cap due to its tightness; patients can acclimate to this by wearing the cap for short periods of time in the days before the testing. There are no cables to connect or technical adjustments to make. Because the task to be run in the iPad tablet will have a game component, we anticipate that younger participants will be particularly happy to engage in this part of the protocol. This will allow us to determine whether a remote device is useful to assess patient evolution. This knowledge will not provide an immediate benefit to the participants of this study, but may represent an important improvement for the follow-up of anti-NMDARe patient recovery in the future, minimizing presential follow-up visits.

- g) Risks of Blood Tests: Risks associated with blood drawing include infection, bleeding, bruising, fainting and discomfort.
- h) Risks of Lumbar Puncture: Although lumbar puncture (spinal tap) is generally recognized as safe, it does carry some risks. These include post-lumbar puncture headache that can last from a few hours to a week or more. Lying flat and drinking fluids helps to relieve this headache. Patient may experience temporary back discomfort or pain, and mild bleeding that may occur near the puncture site. These side effects resolve without treatment. It is possible that patients will not benefit from the lumbar puncture, but for those patients with unfavourable clinical evolution or relapse, NMDAR antibody testing in CSF will help guide therapeutic decisions (antibody titters in CSF, but not in serum, have clinical correlation).

9. Ethics and legal aspects

The study will be carried out in compliance with the Helsinki Declaration (current version, Fortaleza, Brazil, October 2013) and in accordance with the protocol and with the relevant legal requirements, which in this case is Biomedical Research Law 14/2007 of July 3, and Regulation 2017/745 on Medical Products. Informed consent will be obtained for all patients before their inclusion in the study, and their samples stored in the Neuroimmunology Tissue Collection.

10. Data management

Clinical data from patients will be coded. Each patient will be assigned a code. In another separate database, the IP will store the relationship between each code and the patient's medical record number. In all data management softwares used in this project (PsychoPy, CANTAB, GNPT, Dreem 3 for Research) participants will be indexed by their code and never by their personal identification data.

Coded information from patients will be stored in online Redcap database from HCB (redcap.clinic.cat).

Ipads and wearables will be stored at Cellex 3A, Neuroimmunology laboratory.

11. Treatment of data and archiving of registers. Confidentiality of the data

The treatment, communication and transfer of personal data of all participants will comply with EU Regulation 2016/679 of the European Parliament and of the Council of April 27, 2016 regarding the protection of natural persons in terms of to the processing of personal data and the free circulation of data, being mandatory as of May 25, 2018. The legal basis that justifies the processing of your data is the consent given in this act, in accordance with the provisions of the Article 9 of EU Regulation 2016/679.

The data collected for these studies will be collected identified only by a code, so no information will be included that would allow the participants to be identified. Only the study doctor and his collaborators with the right of access to the source data (clinical history), may relate the data collected in the study with the patient's medical history. In the future, the data collected and properly coded may be used also to address other questions relevant for the understanding of NMDARe, and we will request specific consent for this potential prospective use of the data.

The identity of the participants will not be available to any other person except for a medical emergency or legal requirement.

The health authorities, the Research Ethics Committee and personnel authorized by the study promoter may have access to the identified personal information, when necessary to verify data and study procedures, but always maintaining confidentiality in accordance with current legislation.

Only coded data will be transferred to third parties and other countries, which in no case will contain information that can directly identify the participant (such as name and surname, initials, address, social security number, etc.). In the event that this transfer occurs, it would be for the same purpose of the study described and guaranteeing confidentiality.

If a transfer of encrypted data takes place outside the EU, either in entities related to the hospital center where the patient participates, to service providers or researchers who collaborate with us, the data of the participants will be protected by safeguards such as contracts or other mechanisms established by the data protection authorities.

As promoters of the project, we undertake to process the data in accordance with EU Regulation 2016/679 and, therefore, to keep a record of the treatment activities that we carry out and to carry out a risk assessment of the treatments we carry out, to know what measures we will have to apply and how to do it.

In addition to the rights that the previous legislation already contemplated (access, modification, opposition and cancellation of data, deletion in the new Regulation) now participants can also limit the processing of data collected for the project that are incorrect, request a copy or that moved to a third party (portability). To exercise these rights, they should contact the main researcher of the study or the Data Protection Delegate of the Hospital Clínic de Barcelona through [contact]. They also have the right to contact the Data Protection Agency if they are not satisfied.

The data cannot be deleted even if a patient leaves the study, to ensure the validity of the research and to comply with legal duties and drug authorization requirements.

The Researcher and the Sponsor are obliged to keep the data collected for the study at least until 5 years after its completion. Subsequently, personal information will only be kept by the

city center or their health and by the promoter for other purposes of scientific research if the patient has given their consent to do so, and if this is permitted by law and applicable ethical requirements.

12. Management of biological samples

The serum and CSF of the patients will be stored in the Neuroimmunology Tissue Collection (registered in the ISCII with number C0000051 and in the Biobank of IDIBAPS with the number R091217-012). All patients consent to their inclusion in this collection. The samples are coded so that the samples can be related to the clinical information but not to the donor patient.

13 Funding

Fundació La Caixa, Convocatoria Health of Banking Foundation "La Caixa" 2022.

14 Publication policy

We commit to making public the results of the study, whether they are positive or negative.

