4.1 Primary and secondary variables

Description of primary and secondary variables by specific objectives:

1. Clinically characterize the post-acute stage of NMDARe, provide tools to remotely follow cognitive, behavioral and psychiatric deficits, and assess the impact of a cognitive rehabilitation program.

1.1 General clinical data that will be obtained at each visit from all patients include (all primary variables): age, gender, vision condition, handedness, general medical history, allergies, description and duration of symptoms related to NMDARe, treatments, functional status according to modified Rankin Scale (mRS).

1.2 Presential neurocognitive assessment (primary variables): general neurological examination and a battery of 16 tests (with standardized versions adapted for adults and children) encompassing 8 cognitive domains: intelligence quotient, working memory, learning and memory, psychomotor speed, executive functions, selective and sustained attention, language, visuospatial perception.

1.3 Presential psychiatric assessment (primary variables): Structured clinical interview to assess the presence of psychiatric disorders following DSM-IV-TR guidelines (SCID-I for adults and K-SADS-PL for school-age children, psychotic symptoms (Positive and Negative Syndrome Scale, symptoms of depression (Hamilton Depression Rating Scale), symptoms of mania (Young Mania Rating Scale), Global Assessment of Functioning Scale or Children's Global Assessment Scale.

1.4 Remote cognitive assessment (secondary variables): customized panel of 8 tests for 6 cognitive domains covering working memory, learning and memory, psychomotor speed, executive functions, selective and sustained attention. It will be performed using one of the most validated cognitive research software available (CANTAB:

https://www.cambridgecognition.com/cantab/). Our group already has experience working

with it, and our feedback from patients is usually satisfactory. During presential visits, patients will be trained to use the online platform, and once at home they will run the exercises on an iPad that they will borrow from us and return to us after the tests (we will provide a courier service, and the iPad will have all the necessary software installed, ready to use). An experienced neuropsychologist from our team will guide them through the process and supervise the timings.

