Left over samples of blood and CSF that were obtained and stored during the acute stage of the disease (by the time of symptom onset and local hospital admission) will be obtained from the core laboratory (CBD) for patients seen at our center or will be sent to our center from the referring doctors. The diagnosis of NMDARe requires demonstration of antibodies in CSF (serum can be negative); thus, initial CSF studies form part of standard of care in this disease. For the current study, the left-over routine care serum and CSF samples from the 20 recruited patients will be used after their informed consent. For patients followed at our institution, we will take advantage of a regular follow-up visit to inform about the study and obtain their consent. For patients cared for at other hospitals, the referring doctors will explain the possibility of participating in the current study and, if the patients consent, we will contact them to provide further explanations and in such case obtain the informed consent. These acute samples will be tested for the indicated (see below) biomarkers of autoimmunity, inflammation, and neuronal injury. We are a referral center for the diagnosis and study of this disease, and therefore we have ample experience in receiving and handling the samples.

During the post-acute stage (by the time that patients will come to Hospital Clínic de Barcelona), blood and CSF samples will be obtained for identical studies as those performed in the acute stage serum and CSF samples. Two lumbar punctures will be performed, after informed consented, one at the first presential visit (V1) and the other at the last presential visit (V3). Patients will be given the option to opt out of the two spinal taps. Based on the recently published pilot study and extensive experience with the disease, all patients at V1 have cognitive and psychiatric alterations and most still have residual deficits at V3; thus, the CSF studies are important for investigations on biomarkers of disease severity, outcome and prognosis, and for better optimization of therapeutic options.

In addition to human studies, the current project includes an experimental animal model of

NMDARe using active immunization with the NMDA receptor. Thus, human biological samples will not be used in this experimental animal model (detailed later).

6. Selection of participants

Study group

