20 newly diagnosed NMDARe patients (age ≥12 years) will be recruited. Families and patients will be approached during the acute phase of the disease and invited to participate in the study after hospital discharge. Informed consent and general clinical information through a structured questionnaire will be obtained from participants/legal guardians. Identification of patients will be done in (1) our hospitals, (2) through a network of Spanish hospitals, both adults and pediatrics (already in place, specified in the Annex), and (3) the Neuroimmunology lab at HCB/IDIBAPS (referral center for NMDARe). Because NMDARe predominates in women (8:2), it is expected that there will be a female predominance.

Inclusion criteria

Patients \geq 12 years old with NMDARe in the post-acute stage of the disease, \leq 6 months from hospital discharge (acute phase), will be eligible to participate in the study.

Exclusion criteria

They include: inability to obtain informed consent or inability to travel to our center.

External control group

Patients from a pilot study (n=20; follow-up \geq 2 years; HCB/2016/0596) who underwent similar presential visits (without cognitive rehabilitation or remote assessments/tests) will be contacted to extend their follow-up for an additional year. For patients followed up at our institution, we will take advantage of a regular follow-up visit to inform them about the study and obtain their consent. For patients cared for at other hospitals, the referring doctors will explain the possibility of participating in the current study and, if the patients consent, we will contact them to provide further explanations and in such case obtain the informed consent. They will have 2 additional presential visits (as above) 1 year apart, and blood tests. This group will serve as control and will be compared with newly recruited patients (with cognitive rehabilitation/remote tests). They will provide a long-term followup (\geq 3 years) without remote cognitive rehabilitation or tests and will help to assess the impact of these interventions in outcome, and whether immunologic/ inflammatory signatures or signs of neuronal injury (NfL) are chronically present in blood.

7. Treatment and calendar of the study

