Remote cognitive rehabilitation program will be performed through an online validated platform (Guttmann Neuropersonal Trainer [GNPT]: https://gnpt.es/) run by our team. This is a Sanitary Product with CE certification (Producto Sanitario RPS/430/2014; International Patent [PCT/ES2008/00677]) and here will be used within its approved indications. The rehabilitation program will increase in difficulty and decrease in frequency during the first year of follow-up (V1-V3).

Patients/families will be instructed to perform remote cognitive rehabilitation during the presential visits. Patients will be able to use their personal computer and access via an available link and a user code the GNPT platform. In case that they do not have easy access to adequate equipment to access the platform, we will provide the iPad tablet with all the necessary software installed and ready to use to support their training. The indicated frequency of cognitive training is based on results of a recently published pilot study in which patients were followed with only presential visits (no remote visits or cognitive training was provided). The study showed that a slow progressive cognitive improvement occurred in most patients during the 1 year follow-up. However, the improvement was more marked during the first 6 months compared with the last 6 months. This finding suggested that intensive cognitive training (particularly during the first 6 months) could

accelerate recovery and improve outcome. Accordingly, for the current study patients will undergo cognitive rehabilitation twice per week for the first 6 months and once per week for the last 6 months. Similar programs are currently used by our team for patients with multiple sclerosis (along with collaborations with Institute Guttmann, Barcelona). Remote cognitive sessions will take ~45-60min.

Experimental mouse model of NMDARe

These studies are separate from the human studies. The animal study protocol is currently under revision by the CEEA-UB with registration number 420.22, already pre-approved. As indicated, no human biological samples will be used for the experimental animal model. Of note, although the animal studies are independent of human studies, the running in parallel of both sets of investigations will inform on the mechanisms of the disease and may have future treatment and prognostic implications.

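### Section 8.2 attaches the recovery conclusion in each cognitive domain to a trend in the proportion impaired, the weaker of two planned analyses, and does not say which one decides

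*Protocol*

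**What the plan says.** In the Protocol, section 4.1 item 1.2 makes the in-person cognitive assessment a primary variable, with "a battery of 16 tests (with standardized versions adapted for adults and children) encompassing 8 cognitive domains". Section 7 schedules it at baseline (V1), 6 months (V2) and 12 months (V3).

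Section 8.2 then plans three kinds of analysis that bear on recovery:

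- Linear mixed-effects models of the cognitive and psychiatric variables over follow-up, for differences both between and within the two patient groups, with post-hoc comparisons.
- A trend test on a binary status: "The global tendency of recovery of cognitive deficits in NMDARe (proportion of patients compared to the general population in each domain) will be assessed" by Cochran-Armitage.
- Wilcoxon signed-rank and McNemar tests for other comparisons within the disease group.

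The level is common to all: "All analyses will be addressed considering a two-tailed type I error of 5% with statistical significance set at p-value <0.05". No analysis is ranked above another.

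Section 8.1 sets the size at "20 newly recruited NMDARe patients and 20 patients from a previous pilot study for extended follow-up", on feasibility: "Given that NMDARe is a rare disease, we are not able to perform a sample size estimation".

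**The concern.** A proportion of patients compared with the general population requires a yes/no status in each domain. That the underlying results are continuous and norm-referenced is an inference. It is a fair one, since the tests come in standardized versions and the same variables are to be fitted with linear models.

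Reducing a score to a status discards movement that does not cross the cut. The protocol's account of its pilot suggests such movement will be common. Section 7 reports: "The study showed that a slow progressive cognitive improvement occurred in most patients during the 1 year follow-up". Section 5 says that "all patients at V1 have cognitive and psychiatric alterations and most still have residual deficits at V3". The second statement covers cognitive and psychiatric problems together and is not broken down by domain, so it supports the concern only in general terms.

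What is at stake is how objective 1 is answered. If the model shows a domain improving and the trend test is not significant, section 8.2 does not say which result states whether that domain recovered. Its wording points to the trend test.

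**Working it through.** **Figure to reproduce.** None. The protocol gives no power or sample-size calculation for the human study.

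**Inputs from the protocol.** 20 newly recruited patients (sections 6 and 8.1); three visits at 0, 6 and 12 months (section 7); two-sided 5% level (section 8.2).

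**Assumed inputs.** Scores in norm units with SD 1; deficit defined as z below -1.5; V1 mean -1.0, -1.5, -2.0 or -2.5; between-visit correlation ρ of 0.6 or 0.8; 12-month gain of 0.4 or 0.6 SD, three quarters of it by V2; complete data.

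**Step 1: continuous score.** With three equally spaced visits the linear contrast (-1, 0, 1) is the V3 minus V1 change. Its SD is √(2(1-ρ)) and its noncentrality is gain / (SD/√20). A t test on 19 degrees of freedom stands in for the mixed-model contrast.

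- ρ = 0.6, gain 0.4: SD = √0.8 = 0.894; noncentrality = 0.4/(0.894/4.472) = 2.0; power about 48%.
- ρ = 0.8, gain 0.6: SD = √0.4 = 0.632; noncentrality = 0.6/(0.632/4.472) = 4.24; power about 98%.

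**Step 2: what the cut keeps.** The proportion impaired is Φ(-1.5 - mean). For V1 mean -2.5 and gain 0.6:

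- V1: Φ(1.0) = 84%, or 16.8 of 20 patients.
- V3 (mean -1.9): Φ(0.4) = 66%, or 13.2 of 20 patients.

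The average score rises by 0.6 SD, while the net number impaired falls by about 3.6. At ρ = 0.8, power is 45% for the paired binary trend and 98% for the score.

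**Step 3: the two binary tests.**

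- Paired trend, McNemar type: z = (b - c)/√(b + c), where b and c count patients who change status between V1 and V3 in each direction.
- Cochran-Armitage: z = (k3 - k1)/√(2n·p̄(1-p̄)), where k1 and k3 are the numbers impaired at V1 and V3, p̄ is the pooled proportion and n = 20. This treats the visits as independent patients. With no change over time, the true variance of k3 - k1 is 2n·p(1-p)(1-ρb), where ρb is the correlation of the binary status within a patient. The denominator is therefore too large and the test loses further power.

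**Step 4: simulated power over the assumed grid, 20,000 runs per scenario.**

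| Test, 12-month gain 0.4 to 0.6 SD | Power |
|---|---|
| Cochran-Armitage, as planned | 7-28% |
| Paired binary trend | 17-57% |
| Continuous score | 47-98% |

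With no true change, the paired binary test rejects in 2-5% of runs, because it is discrete at n = 20. Part of its shortfall is therefore conservatism. The gap remains where its error is near 5%: at V1 mean -1.5, power is 22% against 48%, and 56% against 98%.

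**Step 5: larger gains.** The gap between paired binary trend and continuous score falls to 6-34 points at 1.0 SD and 1-23 points at 1.25 SD.

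**Step 6: how often the analyses disagree.** This used other assumptions: V1 mean -1.0 or -1.5, cut -1.5 or -2.0, ρ of 0.5 or 0.7, and 65% of the gain by V2. The continuous analysis was a random-intercept linear time trend.

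| | Gain 0.5 SD | Gain 0.8 SD |
|---|---|---|
| Cochran-Armitage power | 10-19% | 24-51% |
| Paired binary trend power | 18-39% | 31-74% |
| Mixed-model power | 58-80% | 93-99% |
| Cochran-Armitage not significant when the mixed model is | 70-88% | 46-76% |

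With no gain, Cochran-Armitage rejects in only 0.6-2.4% of runs here, against a nominal 5%.

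**The case against.** The strongest reply is that the remedy is already planned. Section 8.2 opens with mixed models of the cognitive variables within groups over follow-up, and change over time within the newly recruited group is recovery. Wilcoxon signed-rank tests, which also use the scores, are planned too. This stands, and it limits the harm.

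A reader might infer that the study's whole finding on recovery rests on the cut, so that it would report no recovery while scores clearly improve. The documents do not support that. No rule declares a domain unrecovered when the trend test is not significant, and reaching that report would mean ignoring the mixed model in the same paragraph.

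It can also be said that the proportion still impaired is a question of its own. That stands: if scores rise but most patients stay below the norm, a nearly flat proportion is a correct description. Nor is it a defect that patients above the cut at V1 cannot improve in that domain, since they have no deficit there to recover from. The proportion should stay in the report.

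Finally, the size depends on inputs that the protocol does not give, and with large gains the cut costs little. This also stands. It limits how firmly the size can be stated, but the direction held in every scenario with a true gain.

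The reply leaves one thing open. The text gives the recovery label to the trend test and does not say which result prevails when the two disagree.

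**Conclusion.** The point holds in a limited form. Section 8.2 names the proportion trend as the assessment of overall recovery, beside a more powerful analysis of the same variables, and sets no order between them. For moderate gains of 0.4 to 0.6 SD, under the assumptions listed, the planned test would detect the recovery in about 7-28% of studies and the continuous score in 47-98%.

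Two causes contribute. Dichotomizing accounts for most of the loss, since a correctly paired binary test still reaches only 17-57%. Applying a test for independent observations to repeated visits accounts for the rest. Correcting the pairing alone would therefore not close the gap.

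The consequence is conflicting answers by domain under objective 1. The evidence of improvement itself is not lost. The change is worth making because it is cheap.

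**What to change.** Add to section 8.2 that the recovery conclusion for each domain rests on the visit effect in the continuous domain score among newly recruited patients, from the mixed model already planned, reported as V1-V2 and V1-V3 changes with 95% confidence intervals.

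Report the proportion with a deficit at each visit, with confidence intervals, as a supportive description of how many patients remain impaired. State that its trend test does not decide whether a domain recovered. If the trend is still tested, use a method for correlated binary data.

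The cost is one or two sentences, with no new data, visits or patients. The small downside is that the clinically familiar percentage impaired no longer carries a deciding test.
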